6.2 Dose Delays and Modifications for Cisplatin

Cisplatin will be initially administered at a dosage of 75mg/m² as an IV infusion given every 3 weeks. Patients who experience a Grade 3 or 4 toxicity attributable to cisplatin will have their cisplatin dose reduced to per Table 6-2. Toxicities resulting in myelosuppression, renal insufficiency, ototoxicity, and marked nausea and vomiting are most commonly seen with cisplatin monotherapy. Assessments should be made immediately prior to the scheduled administration of the chemotherapy. If patient needs to discontinue cisplatin therapy, patient can be treated on protocol with AZD1775 monotherapy.

Table 6-2 DOSE MODIFICATION OF CISPLATIN

Dose Level	Cisplatin Dose
0	75mg/m^2
-1	60mg/m^2
-2	50mg/m^2

Dose delays and modifications are summarized in the toxicity table in Table 6-6.

No dose re-escalations are allowed on study, except where noted below.

Expected toxicities for Cisplatin:

Nephrotoxicity

The major dose-limiting toxicity of cisplatin is cumulative nephrotoxicity. Tubular necrosis of both proximal and distal renal tubules has been noted in 28% to 36% of subjects treated with a single dose of 50mg/m^2 . It is first noted during the second week after a dose and is manifested by elevations in BUN and creatinine, serum uric acid and/or a decrease in creatinine clearance. Renal toxicity becomes more prolonged and severe with repeated courses of the drug. Renal function must return to normal before another dose of cisplatin can be given. Nephrotoxicity can be reduced by IV hydration and mannitol diuresis.

Nausea and Vomiting

Cisplatin causes moderate to severe nausea and vomiting in almost all subjects treated. Nausea and vomiting usually begin within 1 to 4 hours after treatment and last up to 24 hours. Various degrees of vomiting, nausea, and/or anorexia may persist for up to 1 week after the treatment. Delayed nausea and vomiting (beginning 24 hours or after chemotherapy) has occurred with complete emetic control on the day of cisplatin therapy. The use of prophylactic and continuing antiemetic medication reduces these adverse effects.

Hypomagnesemia

Hypomagnesemia has been reported in subjects treated with cisplatin and is probably related to renal tubular damage. It may become severe enough to cause tetany. Generally, serum electrolytes return to normal levels when cisplatin is discontinued and supplemental electrolytes are administered.

Ototoxicity

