Ototoxicity has been observed in up to 31% of subjects treated with a single dose of cisplatin (50mg/m²) and is manifested by tinnitus and/or hearing loss in the high frequency range (4000 to 8000 Hz). Decreased ability to hear normal conversational tones may occur occasionally. Ototoxicity can be more severe in children than in adults and more frequent and severe with repeated administration. Hearing loss can be unilateral or bilateral and is usually not reversible. During treatment with cisplatin, it is necessary to monitor hearing at each visit as part of a standard physical exam.

Myelosuppression

Myelosuppression occurs in 25 to 30% of subjects treated with cisplatin. The nadirs in circulating platelets and leukocytes occur between days 18 and 23, with most subjects recovering by day 39. Leukopenia and thrombocytopenia are more pronounced at higher doses (>50 mg/m²). Anemia (a decrease in hemoglobin of 2 gm/100ml) occurs at approximately the same frequency and with the same timing as leukopenia and thrombocytopenia.

Neurotoxicity

Cisplatin neurotoxicity is characterized by peripheral neuropathies, which are sensory in nature but can also include motor difficulties such as reduced deep-tendon reflexes and leg weakness. The symptoms usually occur after prolonged therapy (4 to 7 months). Cisplatin therapy should be discontinued when serious neuropathy develops. The neuropathy, however, may progress

further even after discontinuation of treatment.

Hematologic Toxicity

Dose adjustment at the start of a subsequent cycle of therapy will be based on the neutrophil and platelet counts on day 1 of the cycle. ANC must be $\geq 1.0 \times 10^9 / L$ and platelets $\geq 75 \times 10^9 / L$ before the start of each cycle. Treatment should be delayed to allow sufficient time for recovery. Upon recovery, if treatment is resumed, it should be accounting to the guidelines in Table 6-2 with respect to nadir platelet and ANC values for subsequent cycles, except as noted below. A delay in treatment due to hematologic toxicity if more than 3 weeks will result in withdrawal from the study.

The use of colony stimulating factors (filgrastim or pegfilgrastim) is permissible if recommended by the primary treating physician but should be clearly recorded in the medical record and case report form. Prophylactic use of GCSF is not recommended with the first cycle.

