If GCSF is initiated, then the required dose modification will be adjusted according to the guidelines in footnote of Table 6-3.

Table 6-3
Dose Adjustments for Cisplatin Based on Hematologic Values for Preceding Cycle

Platelets (×1	0 ⁹ /L)	ANC (×10 ⁹ /L)	Dose of Cisplatin
≥75	and	≥1.0	75mg/m ^{2*}
≥50	or	≥ 0.5	60mg/m ^{2*} ,#
< 50	or	<0.5	50mg/m^{2*} ,@
Recurrence of	grade 3 or 4 th	rombocytopenia after 2 dose reductions	Withdraw subject from study
or			continue on ADZ1775
alone			
Recurrence of	grade 3 or 4 ne	utropenia after 2 dose reductions	Withdraw subject from study
or			
			continue on ADZ1775
alone			

^{*} Treatment should be delayed until recovery of platelets to $\geq 100 \times 10^9 / L$ and ANC to $\geq 1.0 \times 10^9 / L$.

Non-Hematologic Toxicity

For other grade 3 or higher non-hematologic effects (with the exception of grade 3 transaminase elevations and nausea or vomiting), treatment should be delayed until resolution (less than or equal to baseline). Treatment can be resumed at 60mg/m², if deemed appropriate by the treating physician, for all subsequent cycles.

Neurosensory Toxicity

[#] For ANC ≥0.5 treat at 75mg/m² dose if initiating GCSF

[@] For ANC<0.5 treat at 60mg/m² dose if initiating GCSF

Adjustments of the cisplatin dose in subjects with neurosensory toxicity are shown in Table 6-4. Cisplatin therapy should be held for grade 2 or higher neurosensory toxicity and should resume with a dose reduction once it has resolved to grade 1.

Table 6-4
Dose Adjustments for Cisplatin Based on Neurosensory Toxicity

CTCAE Grade	Dose of Cisplatin
0-1	100% of previous dose
2	60mg/m^2
3-4	Withdraw participant from study or continue on AZD1775
alone	

Tinnitus or Significant Hearing Loss

In cases of tinnitus or significant hearing loss, cisplatin therapy should be reduced or stopped, at the discretion of the investigator.

Nephrotoxicity

Cisplatin dose adjustments in subjects with renal toxicity are shown in Table 6-5. Either serum creatinine or estimated creatinine clearance may be used. If a dose delay or dose reduction occurs due to nephrotoxicity, subsequent doses of cisplatin may be escalated based on the renal function on the day of treatment (+/- 3 days) and should be determined based on Table 6-5.

Table 6-5
Cisplatin Dose Adjustments for Renal Toxicity

Creatinine(mg/dl)	OR Creatine Clearance(cc/min)	Dose of Cisplatin
<1.6	>50	75mg/m^2
1.6-2	10-50	60mg/m^2
>2	<10	Delay one week

Other Toxicity

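### Table 6-3's 'or' in the middle row and its ANC-only G-CSF footnotes allow a higher resumed cisplatin dose than the lower of the matching Table 6-6 rows

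*Combined protocol and SAP*

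**What the plan says.** All of this is in section 6.2. Counts are ×10⁹/L and doses mg/m² throughout.

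- **Table 6-3**, titled "Dose Adjustments for Cisplatin Based on Hematologic Values for Preceding Cycle", has three dosing rows. Row 1: platelets ≥75 *and* ANC ≥1.0, dose 75. Row 2: platelets ≥50 *or* ANC ≥0.5, dose 60. Row 3: platelets <50 *or* ANC <0.5, dose 50.
- **Its G-CSF footnotes.** Row 2 carries "For ANC ≥0.5 treat at 75mg/m² dose if initiating GCSF" and row 3 carries "For ANC<0.5 treat at 60mg/m² dose if initiating GCSF". The lead-in makes them binding: "If GCSF is initiated, then the required dose modification will be adjusted according to the guidelines in footnote of Table 6-3".
- **Table 6-6** treats the two counts in separate rows. ANC above 1.0: no change; ≥0.5: 60 (75 with G-CSF); <0.5: 50 (60 with G-CSF). Platelets above 100: no change; above 50: 60; below 50: 50. The platelet rows have no G-CSF exception.
- **Status of the two tables.** The text says "Dose delays and modifications are summarized in the toxicity table in Table 6-6". Nothing says which table, or which count, prevails if they differ.
- **Recovery.** The asterisk footnote to Table 6-3 says "Treatment should be delayed until recovery of platelets to" at least 100, with ANC at least 1.0. Section 5.2.2, the hematologic text of section 6.2 and the Table 6-6 platelet rows use 75 for platelets.

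**The concern.** A dosing table should return one dose for each pair of counts. Because row 2 joins its conditions with 'or', a patient with one count in the lowest band and the other higher meets rows 2 and 3 together. A reader who stops at the first row met gives 60, and one who lets the worse count decide gives 50.

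The footnotes raise a second problem that does not depend on the first. G-CSF is support for neutrophils, yet read literally the footnotes lift the dose whatever the platelets were. A reduction that the platelet count alone would require can then be cancelled because G-CSF is started.

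At stake are safety and consistency between sites in the resumed cisplatin dose. Section 6.2 puts myelosuppression at 25 to 30% of cisplatin-treated subjects, with nadirs on days 18 to 23, so low counts around the next planned day 1 (day 22 of a 21-day cycle) are foreseeable. It also says that leukopenia and thrombocytopenia are more pronounced above 50 mg/m².

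**Working it through.** The plan gives no figure to reproduce, so the check is an enumeration of the rows.

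**Inputs.** The rows and footnotes of Tables 6-3 and 6-6, as set out above. Dose levels 0, −1 and −2 are 75, 60 and 50 (Table 6-2). 'No change' is written as 75, and I ignore the difference between > and ≥ at a boundary.

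**Convention.** Both tables are read top-down, first row met, with Table 6-6 applied to each count and the lower result taken. Both tables need a convention. Row 2 of Table 6-3 also contains all of row 1, and in Table 6-6 the ≥0.5 ANC row contains ANC above 1.0 just as the >50 platelet row contains platelets above 100. To expose the overlap, the table below lists every Table 6-3 row met once row 1 has failed.

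**Step 1: no G-CSF, nine cells.**

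| Platelets | ANC | Table 6-3 rows met | Table 6-3 dose | Table 6-6 platelets / ANC | Lower |
|---|---|---|---|---|---|
| ≥75 | ≥1.0 | 1 | 75 | 75* / 75 | 75* |
| ≥75 | 0.5–0.9 | 2 | 60 | 75* / 60 | 60 |
| ≥75 | <0.5 | 2 and 3 | 60 and 50 | 75* / 50 | 50 |
| 50–74 | ≥1.0 | 2 | 60 | 60 / 75 | 60 |
| 50–74 | 0.5–0.9 | 2 | 60 | 60 / 60 | 60 |
| 50–74 | <0.5 | 2 and 3 | 60 and 50 | 60 / 50 | 50 |
| <50 | ≥1.0 | 2 and 3 | 60 and 50 | 50 / 75 | 50 |
| <50 | 0.5–0.9 | 2 and 3 | 60 and 50 | 50 / 60 | 50 |
| <50 | <0.5 | 3 | 50 | 50 / 50 | 50 |

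*60 for platelets of 75 to 100, because Table 6-6 prints 100 as its no-change cut-off.

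Rows 2 and 3 both hold in 4 of 9 cells. First-match reading gives 60 in all four, where the lower Table 6-6 row is 50. Platelets 40 with ANC 2.0 is an example.

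**Step 2: G-CSF started, ANC below 1.0, six cells.**

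| Platelets | ANC | Table 6-3 with footnotes | Lower of Table 6-6 rows |
|---|---|---|---|
| ≥75 | 0.5–0.9 | 75 | 75 (60 if platelets 75–100) |
| ≥75 | <0.5 | 60 | 60 |
| 50–74 | 0.5–0.9 | **75** | 60 |
| 50–74 | <0.5 | 60 | 60 |
| <50 | 0.5–0.9 | **75** (row 2) and 50 (row 3) | 50 |
| <50 | <0.5 | **60** | 50 |

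Two cells are one level too high whether or not the rows overlap: 75 v 60 (for example 60/0.8) and 60 v 50 (40/0.3). A third, 40/0.8, returns 75 or 50, and its two-level gap comes from the overlap. With Table 6-6's printed cut-off of 100, platelets 75–100 with ANC 0.5–0.9 is a further mismatch, 75 v 60.

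**Step 3: effect of the corrections.** If row 2 becomes 'row 1 not met, platelets ≥50 *and* ANC ≥0.5', each of the nine cells returns one dose: 75 in 1, 60 in 3, 50 in 5. With G-CSF and a no-change cut-off of 75 in both tables, mismatches are 3 of 6 as written and 2 of 6 after the row 2 change. They fall to 0 of 6 once the first footnote is limited to platelets ≥75 and the second to platelets ≥50. With a cut-off of 100, 0 of 6 also follows, but only if row 1, the first footnote and Table 6-6 all use 100.

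**The case against.** The strongest reply is that a sensible reader already knows what is meant. If row 3's 'or' is read as 'the worse count governs', every cell without G-CSF has one dose. Table 6-6 puts G-CSF relief under ANC only, and section 5.4 lists colony-stimulating factors under neutropenia, so the footnotes were presumably meant to relax only the ANC-driven reduction. Nobody is dosed at the low counts, G-CSF is optional, and section 6.1 both recommends modifying AZD1775 first and holds or lowers it for thrombocytopenia.

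Much of this stands as evidence of intent. It does not remove the defect. No sentence states the worse-count rule, and the lead-in requires use of footnotes that lack a platelet limit. The recovery rules settle when cisplatin resumes, not at what dose, and the AZD1775 rules do not set the cisplatin dose.

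A reader might infer that Table 6-6 is itself unambiguous and can serve as the reference without further rules. It cannot: its rows are nested too, and at <50 / 0.5–0.9 and 50–74 / <0.5 it lists one row at 60 and one at 50 with no rule for choosing.

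A reader might also infer that the basis for the counts is contradictory. Section 6.2 first says dosing "will be based on the neutrophil and platelet counts on day 1 of the cycle", and then that on resumption "it should be accounting to the guidelines in Table 6-2 with respect to nadir platelet and ANC values for subsequent cycles". If the first meant the day of dosing, the recovery gate would leave rows 2 and 3 unused. The natural reading is that day-1 counts decide whether to delay and nadir counts set the resumed dose, which agrees with the title of Table 6-3. What remains is mainly a wrong reference, since Table 6-2 contains no counts.

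**Conclusion.** The point holds as a correction that should be made to an operative dosing rule. Row 2 overlaps row 3 in 4 of 9 cells, giving 60 or both 60 and 50 where the lower Table 6-6 row is 50. Independently, the G-CSF footnotes give one dose level too much in two cells (75 v 60 and 60 v 50), and in a third band, platelets 75–100 with ANC 0.5–0.9, if the printed cut-off of 100 is used.

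This rests on three assumptions: tables read top-down, the lower of the Table 6-6 platelet and ANC rows as the comparator, and the connectors in Table 6-3 as printed ('and' in row 1, 'or' in rows 2 and 3).

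Two larger conclusions are not supported. The cells are not patient frequencies, which the documents do not give. Nor is the trial's inference touched: the response-rate endpoint, alpha and power are unaffected.

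**What to change.** In one protocol amendment:

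1. Reword Table 6-3 row 2 as 'row 1 not met, platelets ≥50 *and* ANC ≥0.5'. Keep row 3.
2. Have the clinical team choose one platelet cut-off for no reduction (75 or 100). Use it in Table 6-3 row 1, in the first G-CSF footnote and in the no-change platelet row of Table 6-6. Without this alignment the tables still disagree at platelets 75–100.
3. Limit the first G-CSF footnote to platelets at or above that cut-off and the second to platelets ≥50, so that G-CSF relieves only the ANC-driven reduction.
4. State that the lower dose governs when the platelet and ANC rows differ.

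As minor tidying, change the reference in the hematologic text from Table 6-2 to Table 6-3, name the preceding cycle's nadir counts as the basis, and align the platelet recovery gate (100 in the Table 6-3 asterisk footnote, 75 elsewhere).

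The cost is rewording one row, two footnotes and a sentence or two, plus aligning the cut-offs. No new visits, blood draws or data are needed, since the Study Calendar (section 10) already schedules a blood count on day 1 of each cycle.

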5. TREATMENT PLAN

5.1 Treatment Regimen

Treatment will consist of one cycle (21 days) of cisplatin monotherapy (cisplatin 75 mg/m2 IV) followed by combination therapy of AZD1775 plus cisplatin starting 21 days later. AZD1775 will be administered as twice daily oral dosing (AZD1775 200mg po bid) x 5 doses for 2.5 days, in combination with cisplatin 75 mg/m2 IV every 21 days. Cycle length is 21 days long. Treatment will be administered on an outpatient basis. Reported adverse events and potential risks are described in Section 7. Appropriate dose modifications are described in Section 6. No investigational or commercial agents or therapies other than those described below may be administered with the intent to treat the participant's malignancy.

	Regimen Description				
Agent	Premedications; Precautions	Dose	Route***	Schedule	Cycle Length
AZD1775*	See Section 5.4	200 mg	PO	Twice daily x 5 doses From Cycle 2	21 days (3 weeks)
Cisplatin	See Section 5.3.2	75 mg/m2	IV 60 minutes	Days 1 From Cycle 1	

* The participant will be requested to maintain a medication diary of each dose of medication. The medication diary will be returned to clinic staff at the end of each cycle.

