5.2.2 Subsequent Cycles

- ANC must be $\geq 1000/\text{mm}^3$
- Hemoglobin must be ≥9mg/dl
- Platelets must be $\geq 75,000/\text{mm}^3$
- Serum creatinine ≤1.5 x ULN, or measured creatinine clearance (CrCl) ≥45 mL/min as calculated by the Cockcroft-Gault method or 24-hour measured urine CrCl ≥45mL/min
- Transaminitis must return to \leq grade 2
- Diarrhea must be resolved \leq grade 1.
- Nausea and Vomiting must return to ≤ grade 1
- Neurosensory must be \leq grade 2
- Other Treatment Related non-Hematologic Toxicity must return to ≤ grade 1

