6. DOSING DELAYS/DOSE MODIFICATIONS

Dose delays and modifications will be made as indicated in the following table(s). The descriptions and grading scales found in the revised NCI Common Terminology Criteria for Adverse Events (CTCAE) version 4.0 will be utilized for dose delays and dose modifications. A copy of the CTCAE version 4.0 can be downloaded from the CTEP website http://ctep.cancer.gov/protocolDevelopment/electronic applications/ctc.htm.

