Patients who develop treatment-related grade 3 non-hematological toxicity (except grade 3 transaminase elevations and nausea or vomiting) should have cisplatin therapy delayed until toxicity has resolved to less than or equal to grade 1 or baseline. Cisplatin will be continued at 60mg/m² for subsequent cycles. For grade 3 nausea, vomiting, or transaminase elevation, treatment will be delayed until toxicity resolves to grade 1 or less, and treatment may resume at 75 mg/m² dose. If any toxicity, including those described above, results in a three week treatment delay, patients will be taken off protocol. Patients with grade 4 non-hematological toxicity attributed to cisplatin will come off study unless exception is given by the Protocol Chair. Prior to retreatment, toxicity must resolve to less than or equal to grade 1 or baseline. For ≥ grade 2 Hgb toxicity, at the treating physician's discretion, dose may be reduced by one dose level in addition to transfusions and/or growth factor support as clinically indicated, with the option to re-escalate at physician's discretion. This should be documented in the medical record.

Table 6-6: Cisplatin Toxicity Management and Dose Modification Summary Table

Toxicity Event	Dose Modification	
Hematologic		
$ANC > 1000/mm^3$	None	
$ANC \geq 500/mm^3$	Delay until >1000/mm ³ and reduce to 60mg/m ²	
	(treat at 75mg/mm ² if initiating GCSF)	
$ANC < 500/mm^3$	Delay until >1000/mm ³ and reduce to 50mg/m ²	
	(treat at 60mg/mm ² if initiating GCSF)	
Grade 3 or 4 toxicity	Withdrawal from study or continue	
after 2 dose reduction		
Plt >100,000/mm ³	None	
Plt >50,000/mm ³	Delay until >75,000/mm ³ and reduce to 60mg/m ²	
$Plt < 50,000/mm^3$	Delay until >75,000/mm ³ and reduce to 50mg/m ²	
C 1 2 4	W'.1.11.C	
Grade 3 or 4 toxicity	Withdrawal from study	
after dose reduction		
Gastrointestinal		
Diarrhea		
Grade 3/4 or	Delay until resolution and reduce to 60mg/m ²	
requiring hospitalization		
Vomiting, Nausea		
Grade 3/4	Delay until ≤grade 1 or has returned to baseline and resume at	
	75mg/m ² or with one dose reduction (Per investigator discretion)	
Transaminases		
Grade 3/4	Delay until ≤grade 2 and with one dose reduction	
Neurological		
Neurosensory		
Grade 0-1	None	
Grade 2	Delay until resolves to ≤grade 1 and resume with one dose reduction	
Grade 3-4	Withdrawal from study	
Ototoxicity		
Tinnitus or	Reduce dose or withdraw from study at investigator discretion	
significant hearing loss		
Nephrotoxicity		
Cr <1.6 mg/dl or	None	

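### The cycle-start list in Section 5.2.2 accepts grade 2 neurosensory toxicity, while Section 6.2 and Table 6-6 hold cisplatin at grade 2; Section 6 appears to govern, but the day 1 list should say so.

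*Combined protocol and SAP*

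**What the plan says.** **Starting a cycle.** Section 5.2.2 lists the conditions for cycles after the first. The relevant line begins "Neurosensory must be" and sets the limit at grade 2 or lower. It does not say whether it concerns cisplatin, AZD1775 or both. Treatment-related non-hematologic toxicities without a line of their own must be back to grade 1 or lower.

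**Holding cisplatin.** Under Neurosensory Toxicity, Section 6.2 says that cisplatin "should be held for grade 2 or higher neurosensory toxicity and should resume with a dose reduction once it has resolved to grade 1". The grade 2 entry in Table 6-6 begins "Delay until resolves to" and continues with grade 1 or lower, followed by one dose reduction.

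**Dose.** Table 6-2 gives three cisplatin levels: 75, 60 and 50 mg/m2. The grade 2 row of Table 6-4 shows 60 mg/m2, whatever the previous dose, and shows no hold.

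**Which section applies.** Section 5.1 states: "Appropriate dose modifications are described in Section 6". Section 6 opens by saying that delays and modifications follow its tables, and the start of Section 6.2 names Table 6-6 as the summary for cisplatin. Under Other Toxicity, Section 6.2 adds: "Prior to retreatment, toxicity must resolve to less than or equal to grade 1 or baseline". No sentence says what to do where 5.2.2 and 6.2 differ.

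**The concern.** Section 5.2.2 is the list that site staff would naturally check on day 1, and day 1 is when cisplatin is given. For a patient with grade 2 neuropathy, that list raises no objection, while the cisplatin section says to wait. Someone working from the list could treat on a day when the drug should be held.

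The toxicity makes this worth correcting. Section 6.2 describes cisplatin neuropathy as usually following prolonged therapy and warns that it may worsen even after the drug is stopped. Treatment has no fixed number of cycles (Section 5.5), so patients who benefit may stay on cisplatin long enough to develop it. Sites that read the two sections differently would also dose the same patient differently.

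**Working it through.** The plan gives no figure to reproduce here. The check is a comparison of the rules, first by grade and then by previous dose.

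**Step 1. By grade on day 1.**

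| Neurosensory grade | 5.2.2 cycle start | 6.2 text and Table 6-6 (cisplatin) | Table 6-4 row |
|---|---|---|---|
| 0-1 | met | give | previous dose |
| 2 | met | hold to grade 1 or lower, then reduce | 60 mg/m2, no hold in the row |
| 3-4 | not met | Table 6-6: withdraw | withdraw, or AZD1775 alone |

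For giving cisplatin, 5.2.2 and 6.2 disagree only at grade 2.

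**Step 2. Is the looser line merely a restatement?** No. Without a neurosensory line, neuropathy would fall under the 5.2.2 default of grade 1 or lower, which agrees with 6.2. The separate line relaxes that default by one grade. Other lines in the list do track the cisplatin rules: the neutrophil and platelet limits (1000 and 75,000/mm3) match the hematologic text of 6.2, and the transaminase limit (grade 2) and nausea and vomiting limit (grade 1) match Table 6-6. A reader therefore has some reason to treat the list as the cisplatin checklist.

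**Step 3. Does the reference to baseline in 6.2 rescue grade 2?** No. Exclusion 3.2.6 bars neuropathy above grade 1 at entry, so returning to baseline cannot mean grade 2.

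**Step 4. By previous cisplatin dose, on resumption after grade 2.**

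- Previous dose 75: the Table 6-4 row gives 60; one level down in Table 6-2 is also 60, a reduction of (75 - 60)/75 = 20%. The tables agree.
- Previous dose 60: the Table 6-4 row gives 60, a reduction of (60 - 60)/60 = 0%; one level down is 50, a reduction of (60 - 50)/60 = 16.7%. The tables differ by 10 mg/m2.
- Previous dose 50: Table 6-2 has no lower level.

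The 6.2 sentence requires a reduction on resumption, so 50 is the intended answer for the patient at 60. The Table 6-4 row does not show it.

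**The case against.** The strongest reply is that the two rules are compatible. Section 5.2.2 lists necessary conditions for a cycle and nowhere says that meeting them is enough to give cisplatin. A cycle may also consist of AZD1775 alone once cisplatin has been discontinued, which would give a looser cycle-level limit a purpose, although the plan does not state one. The list is looser than Table 6-6 elsewhere too: its diarrhea line begins "Diarrhea must be resolved" and accepts grade 1, while after grade 3 or 4 diarrhea Table 6-6 says "Delay until resolution and reduce to" 60 mg/m2. A site following both sections holds cisplatin, and the references in Sections 5.1, 6 and 6.2 all point to Section 6.

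Most of this stands. It rules out the reading that the plan leaves cisplatin at grade 2 undecided. What remains is that 5.2.2 does not describe itself as a minimum and does not send the reader to 6.2 for neuropathy.

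A reader might go further in three ways that the documents do not support.

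- **That 5.2.2 and Table 6-4 together permit 60 mg/m2 during grade 2 toxicity.** The hold sentence is in the paragraph that introduces Table 6-4, and Table 6-6 repeats the hold. Read in place, 60 is the dose on resumption.
- **That Table 6-4 would raise a patient from 50 to 60, or leave one at 60 unreduced.** Section 6.2 bars re-escalation except where noted, and its noted exceptions concern renal function and hemoglobin. The requirement to resume at a reduced dose excludes the unchanged 60.
- **That the problem can be dated to particular cycles.** The 4 to 7 months in Section 6.2 is the usual onset of symptoms, not of grade 2, and patients may enter with grade 1.

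**Conclusion.** The inconsistency is real and small. Section 5.2.2 accepts one grade more than Section 6.2 and Table 6-6 allow for cisplatin, and the conflict arises only at grade 2. Section 6 most likely governs; this rests on cross-references, because there is no rule of precedence. The practical risk is a site that relies on the 5.2.2 list without consulting 6.2. The mismatch between Tables 6-4 and 6-6 affects only patients already reduced to 60 mg/m2.

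The documents do not say how many patients will reach grade 2 while on cisplatin, so the frequency cannot be estimated. A reader might infer that the efficacy result is at risk. It is not affected as designed: response is defined by RECIST 1.1, the analysis includes everyone who starts the regimen, and the stage 1 and final response cut-offs do not depend on this rule. The change should be made for patient safety and consistent dosing.

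**What to change.** 1. In Section 5.2.2, set the neurosensory criterion for giving cisplatin at grade 1 or lower. Alternatively, keep the line and state that Section 6.2 governs cisplatin holds and that the grade 2 limit applies only to cycles of AZD1775 alone. The existing AZD1775 rules in Section 6.1 need not be restated.
2. In Table 6-4, label the grade 2 row as the dose on resumption after the hold, one level below the previous dose (75 to 60, 60 to 50). Since Table 6-2 stops at 50, the label should also say what happens there.

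The cost is a wording change in one list and one table row, with no effect on sample size, visits or analysis. The clinical downside is that some patients with persistent grade 2 neuropathy will have cisplatin delayed or stopped. Section 6.2 already requires this: it takes patients off protocol when toxicity causes a three-week delay, and it allows AZD1775 alone where cisplatin has to be discontinued.

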CrCl >50 cc/min		
Cr 1.6-2 mg/dl or	50mg/m ²	
CrCl 10-50 cc/min		
Cr>2 mg/dl or	Delay one week	
CrCl <10-cc/min		
Other Toxicity		
Grade 3	Delay until ≤ grade 1 or has returned to baseline and resume at	
	60mg/m^2	
·		

Grade 4	Withdraw from study, unless exception granted by the Principal
	Investigator

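### Section 6.2 and its summary Table 6-6 give conflicting cisplatin rules for renal dose, grade 3 transaminases and platelet recovery

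*Combined protocol and SAP*

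**What the plan says.** Section 6.2 tells sites that "Dose delays and modifications are summarized in the toxicity table in Table 6-6". The rules for each toxicity come before that table, in running text and in Tables 6-3 to 6-5.

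- **Renal.** The Nephrotoxicity paragraph states that "Cisplatin dose adjustments in subjects with renal toxicity are shown in Table 6-5". The middle row of Table 6-5 reads "1.6-2 10-50 60mg/m^2". The matching row of Table 6-6 reads "Cr 1.6-2 mg/dl or 50mg/m"². The list of expected toxicities adds: "Renal function must return to normal before another dose of cisplatin can be given".
- **Transaminases.** For grade 3 nausea, vomiting or transaminase elevation, the Other Toxicity text reads "transaminase elevation, treatment will be delayed until toxicity resolves to grade 1 or less, and treatment may resume at 75" mg/m². The Table 6-6 row for grade 3/4 transaminases reads "Delay until ≤grade 2 and with one dose reduction". Section 5.2.2 also requires recovery only to grade 2 or better.
- **Platelets.** Section 5.2.2 and the Hematologic Toxicity text let a cycle start at 75 × 10⁹/L or above. The Table 6-3 footnote delays treatment until 100 or above. Table 6-6 delays until above 75, but lists no modification only when platelets are above 100.

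A narrower inconsistency concerns AZD1775 in Section 6.1. The opening text leaves re-escalation to the principal investigator, while a bullet under Other Non-Hematologic Toxicities rules it out.

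**The concern.** A summary table is likely to be what a site consults on the day of treatment. If it differs from the rules it summarizes, compliant sites can give different doses or restart at different times, and a deviation cannot be judged consistently.

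The protocol calls cumulative nephrotoxicity the major dose-limiting toxicity of cisplatin. It cites tubular necrosis in 28% to 36% of subjects after one 50 mg/m² dose, and myelosuppression in 25 to 30%. These rules are therefore likely to be needed. Recovery thresholds also affect who stays on treatment, because a three-week delay takes a patient off protocol.

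**Working it through.** No sample size, power or error rate is involved. The check sets the rules side by side and does arithmetic on the doses.

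| Situation | Section 6.2 text or Tables 6-3, 6-5 | Table 6-6 | Section 5.2.2 |
|---|---|---|---|
| Creatinine 1.6-2 mg/dl or clearance 10-50 cc/min | 60 mg/m² (Table 6-5) | 50 mg/m² | Treat if creatinine ≤1.5 × ULN or clearance ≥45 |
| Grade 3 transaminases | Recover to grade ≤1; 75 mg/m² permitted | Recover to grade ≤2; one dose reduction | Recover to grade ≤2 |
| Platelet recovery (× 10⁹/L) | ≥75 (text); ≥100 (Table 6-3 footnote) | >75 | ≥75 |

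**Renal dose.** In Table 6-2, 60 mg/m² is level -1 and 50 mg/m² is level -2, the lowest.
- Cut under Table 6-5: (75 − 60)/75 = 20.0%.
- Cut under Table 6-6: (75 − 50)/75 = 33.3%.
- Gap between the two tables: (60 − 50)/60 = 16.7%.
- At an assumed body surface area of 1.6 to 2.0 m² (not in the protocol): 10 × 1.6 = 16 mg to 10 × 2.0 = 20 mg per dose.

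**Can the renal row be reached?** Yes.
- Section 5.2.2 allows treatment at clearance of 45 or more, so a patient dosed by clearance falls in the row at 45-50.
- The creatinine arm of the gate admits 1.6 mg/dl where the local ULN is at least 1.6/1.5 = 1.07 mg/dl, and 2.0 mg/dl where it is at least 2.0/1.5 = 1.33 mg/dl. The ULN values are assumptions.
- The sentence on renal function returning to normal, if read as a dosing rule, fits neither table, since both give a dose while function is still abnormal.

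**Transaminases.** A patient who has recovered to grade 2 may be treated under Table 6-6 and Section 5.2.2 but must be held under the 6.2 text. From full dose, one place permits 75 mg/m² and the other requires 60, a difference of (75 − 60)/75 = 20%. In Table 6-6 the neighbouring nausea and vomiting row offers the investigator a choice of dose; the transaminase row does not.

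**Platelets.** The recovery thresholds differ by 100 − 75 = 25 × 10⁹/L. Take a patient with platelets of 80, both on day 1 and at their lowest in the previous cycle, and an adequate neutrophil count:
- Section 5.2.2 and the 6.2 text allow treatment now.
- The first row of Table 6-3 gives 75 mg/m², but its footnote holds treatment until 100.
- Table 6-6 lists no modification only above 100, so the patient falls in the next row and is reduced to 60 mg/m².

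The situation is foreseeable. The protocol puts platelet nadirs at days 18 to 23, with most subjects recovered by day 39, and cycles last 21 days.

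**The case against.** The strongest reply is that a careful site could find a workable course. For renal dosing, the Nephrotoxicity paragraph names Table 6-5, both generally and for doses after a renal delay or reduction, and Table 6-6 is only a summary. A mistake toward Table 6-6 gives less cisplatin, not more. For transaminases, waiting for grade 1 and reducing one level satisfies every rule, because 75 mg/m² is permitted and not required. Section 6.2 also opens with a general reduction for grade 3 or 4 toxicity attributable to cisplatin. For platelets, waiting for 100 meets every recovery threshold, and the footnote is the outlier against three places near 75. Section 6.1 requires consultation with the Principal Investigator on some chemotherapy modifications, and Section 12.2 provides committee review of toxicity.

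Much of this is fair. The pointer to Table 6-5 is a good reason to choose 60 mg/m² as the repair, but it does not cancel the 50 printed in the summary. Taking the strictest rule is not an instruction the protocol gives, and it lengthens delays toward the three-week limit. It also leaves the dose unsettled in the platelet example: 75 mg/m² under Table 6-3, 60 under Table 6-6. Consultation does not cover every delay or renal recalculation.

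Three limits stand. The background toxicity rates do not show how often these particular cells would be reached. The sentence on renal function sits in descriptive text and is weak support. The AZD1775 point is minor, since a specific bar can be read as limiting a general permission.

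**Conclusion.** The concern holds, and the protocol is wrong as written. The renal conflict is the firmest: the same laboratory band carries 60 mg/m² in one table and 50 in another, so no dose satisfies both. For transaminases the firm conflict is the recovery grade, 1 against 2; on dose, one place permits what the other excludes. For platelets, one footnote sets a recovery threshold 25 × 10⁹/L above the other three places.

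These are contradictory instructions for a nephrotoxic drug, so they must be fixed. The number of patients affected cannot be derived from the protocol. No effect on the objective response rate, type I error or power is claimed. The milligram gap rests on the assumed body surface area and the creatinine route on the assumed ULN; the route through clearance of 45-50 needs neither assumption.

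**What to change.** Amend Sections 5.2.2, 6.1 and 6.2 so that each toxicity has one rule:

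- **Renal:** change the Table 6-6 row to 60 mg/m² to match Table 6-5, or have the investigators set both to 50. Align the sentence on renal function returning to normal with the Section 5.2.2 gate.
- **Transaminases:** use one recovery grade and one resumed dose in Section 5.2.2, the 6.2 text and Table 6-6.
- **Platelets:** use one threshold in Section 5.2.2, the 6.2 text, the Table 6-3 footnote and Table 6-6, including the Table 6-6 row that lists no modification.
- **AZD1775:** state whether the bar on re-escalation under Other Non-Hematologic Toxicities overrides the general permission.

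Until the amendment takes effect, add one sentence to Section 6 naming the table that governs. The cost is a text amendment, with no added procedures, visits or patients.
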